### **App and Device Setup**

Participant device accounts that require email address to complete sign up will use study-generated email accounts:

Format: ACT1ON-(3-digit site number)-(3-digit participant number at site)@gmail.com

Example: [contact]

### **Setting up Study ID:**

After informed consent form and all other applicable consenting documents have been signed, a participant ID number will need to be created by study team prior to performing any testing procedures for the study.

The ACT1ON protocol uses the following format when assigning participant ID numbers:

- Protocol designation prefix – 'ACT1ON' for this study
- Site number (###) – site number (same for each protocol) – always 3 numbers
  - Stanford site number = 000
  - UNC site number = 111
- Patient number at site (###) – always 3 numbers
  - Example (for Stanford): ACT1ON-000-001

- Example (for UNC): ACT1ON-000-001

Each site will have prepared login credentials for 10 subjects.

## Garmin Connect App Download

- The Garmin Vivosmart 4 uses the Garmin Connect app. The app is available for iOS on the App Store and Android on Google Play. See below for Garmin Connect App setup.

## Create Account for Garmin Connect

- Each participant will have a Garmin Connect account to record his or her activity
  - Open Garmin Connect App
  - Press “Create account”
  - Allow participant to review legal terms and conditions
  - Enter participant ID in “name” field
  - Enter study email address in “email address” field
  - Enter assigned study password in “password” field
  - Bring physical activity watch in close range to participant’s smartphone so device can connect
  - Allow participant to follow on-screen tutorial on physical activity watch and app
  - When prompted, select preferred display orientation (portrait or landscape)
  - Select watch face that shows heart rate

[figure not shown]

Watch face (above) shows:

- 1) Current heart rate
- 2) Resting heart rate zone

## Garmin Use

- Double tap touchscreen to wake the device up
- Note: screen turns off when not in use
  - Device is still active and recording data when screen is off
- The device should be secured above the wrist bone and not move while running or exercising
- Watch should be worn on non-dominant wrist

## Log an Exercise

The participant should log exercise through the Garmin physical activity wearable.

Participant can record a timed activity, which can be saved and sent to their Garmin Connect account.

[figure not shown]
Press  to view the menu.

Select .

Swipe to scroll through the activity list, and select an option:

- Select  for walking.
  - Select  for running.
  - Select  for strength training.
  - Select  for a cardio activity.
  - Select  for a bike activity.
  - Select  for an elliptical trainer activity.
  - Select  for a Toe-to-Toe™ step challenge.
  - Select  for pool swimming.
  - Select  for a yoga activity.
  - Select  for a stair stepper activity.
  - Select  for other activity types.
- Double tap touchscreen to stop and resume activity timer
  - Tap to view additional screens which appear at top of touchscreen
  - After participant completes activity, double tap touch screen to stop timer
  - Select an option:
    - Select  to save the activity.
    - Select  to delete the activity.
    - Select  to resume the activity.

## Syncing Your Data with Garmin Connect Mobile App

- Garmin device automatically syncs data with Garmin Connect Mobile app each time the app is opened
- Garmin device periodically syncs data with Garmin Connect Mobile app automatically
- Can also manually sync data at any time
  - o Bring device near smartphone
  - o Open Garmin Connect app
  - o Press  to view the menu
  - o Select 
  - o Wait for data to sync
  - o View current data in Garmin Connect app

## Preparing Garmin for Re-Assignment

- Garmin watch will be mailed back to clinic after every 2-week data collection period is complete (refer to timeline above)
- Previous personal data on the Garmin device should be erased prior to assignment of the next participant
  - o Press  to view Menu
  - o Select  >  > **Reset**.
  - o Select the following option:
    - To reset all of device settings to factory default values and delete all user-entered information and activity history, select **Delete Data and Reset Settings**
  - o Press 
  - o Select .
- Garmin Connect app should also be deleted from participant's smartphone at the end of final study visit

### Other Notes

- Garmin Vivosmart 4 should be worn on the same wrist at all times
- Suggestions for optimal charge time include overnight since we are not collecting sleep data
- Keep device on flat surface like a countertop when not in use
- If patient prefers, can charge device ~30 mins daily when sitting (not preferred)
- The device withstands pressure equivalent to a depth of 50 m and is waterproof
- Can be worn for swimming and showering, but preferably not scuba diving or highspeed watersports
- Clean device with a cloth dampened with mild detergent solution and wipe dry after watch is returned
- Make sure device is completely dry before placing on wrist. Avoid chemical cleaners, solvents, and insect repellents that can damage the plastic components and finishes
- Thoroughly rinse device with fresh water after exposure to chlorine, salt water, sunscreen, cosmetics, alcohol, or other harsh chemicals
- Full manual for Garmin Vivosmart 4 provided here:  
[https://www8.garmin.com/manuals/webhelp/vivosmart4/EN-US/vivosmart\\_4\\_OM\\_EN-US.pdf](https://www8.garmin.com/manuals/webhelp/vivosmart4/EN-US/vivosmart_4_OM_EN-US.pdf)

Statistical Analysis Plan

ACT1ON Phase 2 (SMART Pilot) and Phase 3 (Efficacy Trial Development)

NCT03651622

January 20th, 2022

Analytic approach: The overarching objective of this study was, in addition to comparing three dietary approaches for co-management of glycemia and weight among young adults with type 1 diabetes, to identify individual-level characteristics that might drive response to a particular diet approach. Due to the COVID-19 pandemic, we recruited n=68 instead of the planned n=72 study participants, which led to the following changes in our analytic plan:

The updated analytic plan consists of the following descriptive and modeled approaches:

- Pre-COVID diet period 1 (Randomization 1): Model outcomes using generalized linear models (PROC GLM) in SAS due to lack of repeated measures
- All data, both pre- and post-COVID: Generalized estimating equations (PROC GEE) in SAS accounting for repeated measures
- Response variables for all models: Change for each of three diet periods for each of the primary and secondary outcomes:
 - o Primary outcomes:
 - Weight (kg)
 - Hemoglobin A1c (%)
 - Percent time in clinical hypoglycemia (54-60 mg/dL)
 - o Secondary outcomes:
 - Body fat percentage
 - Percent time in target glucose range (70-180 mg/dL)

Pre-COVID, diet period 1 (Randomization 1) only:

- Descriptive analysis
 - o Change in primary and secondary outcomes for each diet period *irrespective of diet* (PROC MEANS in SAS), paired t-test for overall changes in outcomes.
 - o Examine change in primary and secondary outcomes separately for each diet assignment in each of the three diet periods (PROC MEANS in SAS, paired t-test for each diet).
- Modeled analysis (PROC GLM in SAS)
 - o Change in primary and secondary outcomes for pre-COVID diet period 1 according to randomized diet assignment, and adjusted for site, baseline level of the outcome, and gender, which was imbalanced across diet assignments at baseline. Use this model to test for differences between diets.

All data, both pre- and post-COVID:

- Descriptive analysis

- Change in primary and secondary outcomes for each diet period (i.e., each randomization) *irrespective of* diet (PROC MEANS), paired t-test for overall change in outcomes
 - Examine change in primary and secondary outcomes separately for each diet in each of the three diet (i.e., randomization) periods (PROC MEANS, paired t-test for each diet) and look at mean differences between diets (PROC MEANS).
 - Examine change in primary and secondary outcomes separately for each site and each gender in each of the three diet (i.e., randomization) periods (PROC MEANS, paired t-test for change within each stratum per diet period).
- Modeled Analysis (PROC GEE in SAS)
- Change in primary and secondary outcomes between diet periods (i.e., randomization periods) accounting for diet assignment and adjusted for site, the baseline level of the outcome, duration (months) between each diet period given that duration varied widely during the pandemic, a COVID indicator (yes/no), diet period (1, 2, or 3), and gender.

Planned analysis: consider analytic approaches that will allow for identification of individual-level characteristics that may predict individual response to a given diet assignment.

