## 7. Randomization

*Sequential randomization (Baseline, ~3 months, and ~6 months).* At the start of the study, diet randomization schemes will be determined by computer for each individual.

Permuted block randomization with blocks of size 24 will be used to assign all 12 potential treatment regimes using R statistical software. This will be confidentially generated by the statistician and placed into CDART data management software to be revealed only at the point of treatment (diet) assignment for each patient.

Following the baseline data collection and a short run-in period, the initial diet randomization will be revealed to the participant. Based on a priori decision rules at 3 and 6 months post-initial randomization, those for whom the diet assigned is not acceptable or is not effective will have the next diet assignment revealed (be re-randomized). A total follow-up time of 10.5 months allows for evaluation of the effect of the diets on initial weight loss and on early maintenance of initial weight loss. The decision criteria for re-randomization (Table 7.1) will incorporate both clinical outcomes (glycemic control and weight change) and acceptability of the diet to the participant as indicated on the Diet Acceptability Form.

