## 11. Statistical Considerations

We will primarily compare the 3-month response rates to each of the three initial diets using standard statistical comparison procedures (e.g., t-tests and ANOVA) for differences in glycemic control (HbA1c and percent time in hypoglycemia) and change

in weight. In addition, we will conduct a series of secondary, hypothesis-generating analyses using standard statistical approaches as well as more complex fixed and mixed effect regression methods such as generalized additive models and random forests for these outcomes plus body fat and fat free mass. We will compare all diet sequences (there are 12) using the same outcomes and will incorporate evaluation of measures of ingestive behaviors. After adjusting for multiple comparisons, the proposed sample size of n=84 is sufficient to ensure 60% power to detect a moderate effect size (Cohen h=0.68) and 80% to detect a large effect size (Cohen h=0.85) at a significance level of 0.10 for comparing response rates among the 3 diets. Based on data reported in Wing et al (2016) and Russell et al (2014) and other preliminary data, we estimate for the same significance level and with 80% power that we will be able to detect a difference of about 3.0kg for weight change, 1.3% for HbA1c change, and 1.3 percentage point change in percent time <70mg/dl. Here we emphasize that, by design, our primary goal for this pilot work is to inform the final efficacy design, and we have therefore not designed this pilot SMART to be fully powered for all analyses.

An advantage of SMARTs is that they allow for efficient estimation of precise (i.e., deeply tailored) diet strategies. A precise diet strategy adapts treatment to the evolving health status of each participant. We will use a regression-based approximate dynamic programming algorithm known as Q-learning to estimate the precise diet strategy that maximizes weight loss while improving suboptimal or maintaining good glycemic control over the duration of the trial. The form of this estimated optimal diet strategy will generate hypotheses about how best to choose and adapt diets to individual patients. This will require the use of SMART analysis methods for balancing competing outcomes.

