Moreover, we will in fact be able to make valid intent-to-treat comparisons across the three starting diets using the outcomes at 9 months, based on the fact the SMART designs have greater power for intent-to-treat hypotheses than traditional randomized designs (see Chapter 3 of Kosorok and Moodie, 2016). In a standard, randomized trial, failure of a diet would lead to either patient drop-out or switching of diet by the clinician. Thus two sources of bias arise: one from drop out and one from change in treatment. In contrast, with our design, we make additional diet assignments at 3 and 6 months based on diet success. We use randomization instead of ad hoc reassignment. Thus, our design more formally addresses both patient drop out and treatment changes by including diet changes in our design in a balanced way. There may still be some drop out, but it will be lower since patients do not have to leave the study to have their diet changed. Thus the design is adequate to achieve the stated objectives.

In addition, the Q-learning methodology will permit us to pool the data for regression models across similar branches among the possible treatment paths. To illustrate this, we point out that, as described in Chapter 17 of Kosorok and Moodie, 2016, Q-learning is done through a backwards iteration of regression model fitting, with different

regression models at each potential randomization point. In our setting, we can integrate the multiple possible regression models at the third decision time (6 months) into one regression model by including past diets in the history variables as well as by allowing for four treatment options, one for each of the three diets and one for those patients who stay on with the previous diet. We can similarly integrate across the regression models at the 3 month decision time and also at baseline, resulting in the need for only three regression models. We will therefore have sufficient power for all of our proposed analyses. In addition, we will have sufficient sample size to use the pilot data to sample size a full SMART design using the methods described by Laber et al., (2016).

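### The SAP analyses change per diet period only and drops the protocol's long-term comparison by randomized starting diet, so no randomized long-term contrast is estimated.

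*SAP*

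**What the plan says.** **SAP.** The response is set once for everything that follows: "Response variables for all models: Change for each of three diet periods for each of the primary and secondary outcomes". Two models use it.

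- The PROC GLM takes "Change in primary and secondary outcomes for pre-COVID diet period 1 according to randomized diet assignment" and tests differences between diets.
- The PROC GEE, on all data, takes "Change in primary and secondary outcomes between diet periods (i.e., randomization periods) accounting for diet assignment and adjusted for site", and also adjusts for baseline level of the outcome, duration, a COVID indicator, diet period and gender. It names no starting-diet term.

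The descriptive items are also per period: all diets together, by diet, by site and by gender. The SAP attributes its changes as a whole to recruiting 68 rather than 72 participants because of COVID-19.

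**Protocol.** Section 7 (Randomization) states: "Permuted block randomization with blocks of size 24 will be used to assign all 12 potential treatment regimes". It justifies 10.5 months of follow-up by "evaluation of the effect of the diets on initial weight loss and on early maintenance of initial weight loss". Section 11 (Statistical Considerations) sets the primary comparison at 3 months: "We will primarily compare the 3-month response rates to each of the three initial diets". It adds: "We will compare all diet sequences (there are 12) using the same outcomes". Later in the same section, in defence of the design, it says the trial allows "valid intent-to-treat comparisons across the three starting diets using the outcomes at 9 months".

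**The concern.** Table 7.1 of the protocol moves a participant to another diet on less than 2% weight loss since the previous visit, on worse glycemic control, or on an unacceptable diet. In periods 2 and 3 each current-diet group therefore combines people who stayed because they responded with people who arrived because an earlier diet failed. A contrast between current diets in those periods is no longer a comparison of groups formed by randomization alone.

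Starting diet, and the full regime assigned at the outset, remain randomized to the end of the study. A comparison at Visit 4 by starting diet answers a different and useful question: where participants end up when a given diet is tried first and the re-randomization rule is then applied. It also bears directly on early maintenance of weight loss, since regain after an initial loss appears in a baseline-to-Visit 4 difference but is spread over separate period results in the SAP. Without it, the pilot reports no randomized evidence beyond the first period.

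**Working it through.** **1. Is the comparison anywhere in the SAP?** The protocol's 9-month outcome is taken to be Visit 4, which the Appendix 1 timeline places at month 10.

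| Protocol comparison | Place in the SAP |
|---|---|
| Starting diets at 3 months (primary, Section 11) | GLM for period 1, pre-COVID data only |
| Starting diets at 9 months, intent to treat (Section 11) | None |
| The 12 regimes (Section 11) | None |

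The SAP's paired t-test for overall change sits under an item that is per diet period and irrespective of diet. There, overall most naturally means all diets combined, not baseline to Visit 4.

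**2. Is the starting-diet contrast randomized at Visit 4?** The 12 regimes listed in Section 11 divide into four beginning with each diet. With the SAP's 68 participants, that is 68/3 = 22.7 per starting diet, assuming balance and that all 68 were randomized.

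**3. Can the per-period results stand in for it?** An illustrative simulation of 300,000 participants used assumed values: 95 kg starting weight; one diet better by 1.5 kg in period 1, with its effect multiplied by 0.7 and 0.5 in periods 2 and 3; a switch if loss is under 2%; 43% not responding at the first decision.

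- Visit 4 minus baseline, better starting diet against reference: −1.99 kg.
- Sum of the three current-diet contrasts: −1.54 − 1.01 − 0.80 = −3.35 kg.
- With no diet effect, both are about zero.

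The built-in effects add to −1.5 × (1 + 0.7 + 0.5) = −3.30 kg. So in this example the gap comes almost wholly from the two quantities being different estimands: the starting-diet total includes switching. It is not a measure of confounding.

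**4. Precision of the added contrast.** The documents give no figure for a Visit 4 contrast. The nearest are the Section 11 figures for 3 months at significance level 0.10 after an unnamed multiplicity adjustment. Assuming Bonferroni over three pairwise comparisons, two-sided, power = Φ(h√(n/2) − 2.128):

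| Total N (per diet) | h = 0.68 (stated 60%) | h = 0.85 (stated 80%) |
|---|---|---|
| 84 (28) | 66.1% | 85.4% |
| 72 (24) | 59.0% | 79.3% |

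The stated figures fit 72, not 84. That is a separate matter; here it only brackets the SD. The stated detectable weight difference of 3.0 kg at 80% power implies SD = 3.0 / [(2.128 + 0.842) × √(2/n)], which is 3.50 kg at n = 24 and 3.78 kg at n = 28.

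The SD of change over about 10 months is not given. Assuming 4 to 6 kg, the 95% half-width is 1.96 × SD × √(2/22.7):

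| SD (assumed) | Half-width |
|---|---|
| 4 kg | 2.33 kg |
| 5 kg | 2.91 kg |
| 6 kg | 3.49 kg |

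An assumed 20% loss to Visit 4 multiplies these by 1/√0.8 = 1.118, giving 2.60 to 3.91 kg. If the implied 3-month SDs of 3.50 to 3.78 kg still applied, the difference detectable with 80% power at 68 participants would be 3.09 to 3.33 kg, or up to 3.73 kg with 20% loss.

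**The case against.** The strongest reply is that little was promised. The 9-month sentence in Section 11 says what the design makes possible, within an argument for its adequacy. The primary comparison is at 3 months, effect sizes are to be estimated from 3-month means, and the protocol says the pilot is not fully powered for all analyses. This stands as to importance: the omission is of a secondary estimand. It does not explain why a comparison used to defend the design, and a regime comparison stated as planned, both disappear. Recruiting four fewer participants is not a reason specific to either.

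A reader might go further in four ways that the documents do not support.

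- *That starting diet is the only long-term contrast protected by randomization.* The 12 regimes are randomized too, and participants switched at Visit 2 receive one of two untried diets from their randomized scheme. The SAP's pooled diet term does not isolate either comparison.
- *That no estimate of total change can be had.* The SAP does not define the start point of change. If it is study baseline, period 3 change is total change. If it is visit to visit, the three period means can be added in completers. What cannot be recovered from these results is the total by starting diet.
- *That the full trial cannot be sized.* No section says sizing will rest on the SD of 10-month change, and that SD can be computed from the collected data at any time.
- *That the later-period contrasts are known to be badly biased.* The documents give no basis for a size, and the simulation does not supply one.

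Two technical cautions also stand. Months since baseline is a post-randomization variable, so adjusting for it in the main model would weaken the case for the contrast. For participants who straddled April 2020, weight moved from clinic to home scale and HbA1c to home kits and another laboratory, so Visit 4 minus baseline crosses measurement methods. Drop-out may also bias the contrast, beyond widening its interval.

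**Conclusion.** The point holds as an unexplained omission of a secondary analysis. The SAP estimates no randomized contrast beyond pre-COVID period 1, although the protocol describes one by starting diet and plans another by regime. The primary 3-month comparison is not lost through this omission.

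The gain from adding the starting-diet contrast is modest: a randomized long-term estimate with a 95% half-width of about 2.3 to 3.5 kg for weight, diluted by switching. That range assumes an SD of 4 to 6 kg, all 68 participants randomized in balance, and no drop-out. It describes the precision of the remedy, not the size of an error in the present plan.

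**What to change.** Add to the SAP, for weight, HbA1c and percent time in hypoglycemia, one model of Visit 4 minus study baseline by starting diet as randomized, adjusted for site, baseline value and gender.

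- Report estimates with confidence intervals and the SD of total change, with no efficacy claim.
- Label the contrast as the effect of starting diet including later re-randomization.
- Report the number with Visit 4 data by starting diet.
- Add elapsed time and a COVID or virtual-visit indicator in a sensitivity analysis only, since both arise after randomization.
- Define the start point of change for every per-period analysis.
- State why the regime comparison was dropped. If the starting-diet comparison is also to stay out, give the reason for that.

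The cost is one model per outcome, plus a sensitivity version, on data already collected. The downside is a wide interval that could be over-read, which the labelling and the absence of an efficacy claim are meant to prevent.

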Study Duration	
Each subject's participation will last approximately 10.5 months.

	Study data collection is expected to end by November 2020. Grant funding ends April 2021.
Study Phases	1. Screening : screening for eligibility, recruiting and obtaining consent 2. Intervention : study intervention (randomization to diets) (Note: Each clinical site will recruit approximately four participants a month over 12 months. Intervention will be ongoing once enrollment has begun.)
Efficacy Evaluations	Glycemic control: HbA1c and percent time in hypoglycemia (continuous glucose monitor worn for 14-days at each measurement visit). Change in weight.
Safety Evaluations	Participants will be asked about hypoglycemic events at each study visit and RD session (in person and telephone). The RDs will communicate regularly with the study endocrinologist to review labs and self-monitored blood glucose (SMBG) data to ensure appropriate insulin dosing.
Statistical and Analytic Plan	We will primarily compare the 3-month response rates to each of the 3 initial diets using standard statistical comparison procedures (e.g., t-tests and ANOVA) for differences in glycemic control (HbA1c and percent time in hypoglycemia) and change in weight.  In addition, we will conduct a series of secondary, hypothesis-generating analyses using standard statistical approaches as well as more complex fixed and mixed effect regression methods such as generalized additive models and random forests for these outcomes plus body fat and fat free mass.
Data and Safety Monitoring Plan	Data quality and safety monitoring will occur both within the research team (data quality committee) (monthly) and a 4-member DSMB (to meet twice yearly).  Participant accrual and retention, progress, completeness of standardized measures, and attendance at intervention sessions will be monitored. All aspects of data collection and data storage will be carefully monitored to ensure rapid detection of errors, inconsistencies or other problems. Distributions of key variables will be monitored for data quality and safety. AE and SAE, as defined by NIH, will be reported to the local site investigator and corresponding IRBs. AE/SAEs will be reviewed monthly.

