### 3. Study Objectives

Our main overall objective is to develop a rigorous adaptive design to test the efficacy of a behavioral intervention to simultaneously optimize glycemic control and facilitate weight management among overweight young adults with T1D. We propose **Specific Aims** in three phases focused on young adults (age 19-30 years) with T1D. ***This protocol covers Aim 2 (Study Phase 2).***

**Aim 2, Phase 2:** Phase 2 is an initial pilot and feasibility study using a Sequential, Multiple Assignment, Randomized Trial (SMART) design to identify acceptable and effective dietary strategies to optimize both glycemic control and weight management in young adults with T1D. This pilot trial will include 84 randomized participants (42 at UNC, 42 at Stanford) in a 10.5 month behavioral intervention, with co-primary outcomes of glycemic control (HbA1C and hypoglycemia) and weight loss. (Note: data from Aim 1 Phase 1, approved under separate IRB approval, will inform the SMART pilot. Phase 1 Study 1 will inform calorie goals. Phase 1 Study 2 will inform potential counseling strategies related to dietary response to hypoglycemia.)

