Additionally, participants will be queried regarding occurrence of both non-severe and severe hypoglycemia by their RD at each encounter (check-in and longer remote sessions). Participants will also be queried regarding increased hypoglycemia on the short and long diet acceptability forms, completed between and at measurement visits. Consistent with a recent report on consensus guidelines for the use of continuous glucose monitoring, contributed to by MPI [name], we define hypoglycemia as CGM-based glucose <70mg/dl for more than 10 min, not requiring help from another person.

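### The SAP's only hypoglycemia outcome is percent time at 54-60 mg/dL, where the protocol uses time below 70 mg/dL; correcting 60 to 70 would still leave out time below 54

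*SAP*

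**What the plan says.** The protocol makes hypoglycemia part of the primary endpoint set. Section 3 describes the pilot as one "with co-primary outcomes of glycemic control (HbA1C and hypoglycemia) and weight loss". The Synopsis, under Efficacy Evaluations, names the measure as "percent time in hypoglycemia (continuous glucose monitor worn for 14-days at each measurement visit") and gives no threshold there. The threshold appears in two other places:

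- Section 8a: "we define hypoglycemia as CGM-based glucose <70mg/dl for more than 10 min, not requiring help from another person".
- Section 11, in the detectable-difference statement at 80% power: "1.3 percentage point change in percent time <70mg/dl".

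The SAP (January 2022) lists three primary outcomes: weight, HbA1c and "Percent time in clinical hypoglycemia (54-60 mg/dL"). Its only other CGM outcome, a secondary one, is "Percent time in target glucose range (70-180 mg/dL"). The primary and secondary outcomes are the response variables for every SAP model. The single reason the SAP offers for changing the analysis is that "we recruited n=68 instead of the planned n=72 study participants, which led to the following changes in our analytic plan".

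**The concern.** A 6 mg/dL band with a floor at 54 is not the variable the protocol describes. Time below 54 and time from 60 to 70 fall in neither the primary band nor the 70-180 range. Recruiting 68 instead of 72 participants cannot explain a new glucose range, and no other reason is given.

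The estimate of a co-primary outcome is at stake. The GLM that tests differences between diets and the GEE model would both be run on the narrow band. Section 3 says the pilot is meant to estimate the improvement in hypoglycemia for each diet to inform a fully powered SMART, so the wrong variable would carry into the next design. The 1.3-point detectable difference in section 11 does not apply to the band.

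Safety surveillance is not at stake. Re-randomization (Table 7.1) uses self-reported hypoglycemia, and sections 8a, 12 and 14 provide for events to be asked about, reviewed and monitored separately.

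**Working it through.** **1. The definitions side by side.** Time below 70 = (below 54) + (54-60) + (60-70).

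| Range | Protocol, below 70 | SAP as printed, 54-60 | If 60 should read 70 |
|---|---|---|---|
| below 54 | counted | omitted | omitted |
| 54-60 | counted | counted | counted |
| 60-70 | counted | omitted | counted |

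The mismatch follows from the text alone, on either reading of the SAP. The remaining steps only gauge its size.

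**2. The plan's own figure.** The 1.3-point difference cannot be reproduced, because the documents give no SD for percent time below 70. The SD it implies at n = 84 (28 per diet) is SD = 1.3 / [(z_alpha + z_power) x sqrt(2/28)].

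- Two-sided 0.10, unadjusted: 1.3 / [(1.645 + 0.842) x 0.267] = 1.96 points.
- Two-sided 0.10/3 (an assumed adjustment; the plan names none): 1.3 / [(2.128 + 0.842) x 0.267] = 1.64 points.

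These SDs belong to time below 70 and say nothing about the SD of time at 54-60. Even for the protocol's own measure, moving from 84 to 68 participants at the same SD takes 1.3 to 1.3 x sqrt(84/68) = 1.44.

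**3. Share of time below 70 in each band.** The assumption, which is not in the documents, is log-normal glucose with mean 150, 165, 180 or 200 mg/dL and CV 36, 42 or 48% (12 combinations). With s² = ln(1 + CV²) and m = ln(mean) - s²/2, time below x is Phi[(ln x - m)/s].

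One combination worked through, mean 165 and CV 42%: s = 0.403, m = 5.025.

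- Below 54: Phi(-2.570) = 0.51%.
- Below 60: Phi(-2.308) = 1.05%.
- Below 70: Phi(-1.926) = 2.71%.
- The 54-60 band is 1.05 - 0.51 = 0.54 points, or 20% of time below 70. Time below 54 is 0.51/2.71 = 19%. The 54-70 band is 81%.

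Ranges over the grid, with a gamma distribution at the same means and CVs for comparison:

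| Share of time below 70 | Log-normal | Gamma |
|---|---|---|
| 54-60 | 15-21% | 18-20% |
| 60-70 | 50-77% | 36-58% |
| below 54 | 8-30% | 23-46% |
| 54-70 | 70-92% | 54-77% |

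**4. The 1.3 points on the SAP's scale.** If a change spreads over the bands in proportion to these shares (a further assumption), 1.3 points of time below 70 becomes, under the log-normal, 1.3 x 0.154 = 0.20 to 1.3 x 0.206 = 0.27 points at 54-60. For 54-70 it becomes 1.3 x 0.704 = 0.92 to 1.3 x 0.924 = 1.20. In four of the 12 log-normal combinations total time below 70 is itself under 1.3% (0.23, 0.57, 0.81 and 1.13%), so a 1.3-point reduction cannot occur there. Over the other eight the ranges are 0.24-0.27 and 0.92-1.13.

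**The case against.** **A slip of one digit.** The SAP's target range starts at 70, so 54-60 leaves 60-70 unassigned, and 54-69 or 54-70 is a plausible intended band. That is fair, but nothing in the text confirms it. If it is right, the loss of 60-70 disappears and the omission below 54 remains.

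**The time is not wholly lost.** A minute below 54 or at 60-70 is a minute outside 70-180, so it lowers the secondary outcome. That stands. There, however, it is mixed with time above 180 and cannot be read as hypoglycemia. Section 8b also allows other CGM measures to be explored, without naming one that fills the gap.

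**Section 8a defines episodes.** The 10-minute condition and the exclusion of events needing help suggest a definition of non-severe episodes, not of percent time. That also stands. The comparison then rests on section 11, which states percent time below 70 outright.

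**The magnitude is assumed, and the direction is probably safe.** The share below 54 runs from 8% to 46% across the two shapes, so what survives a typing correction is poorly determined. Across the assumed populations, 54-60 time tracks below-70 time almost perfectly (correlation 0.9998 log-normal, 0.998 gamma). That is not a correlation across participants, but it gives no support to an expectation of reversed diet conclusions. Time moving from 54-60 to below 54 would register as improvement, yet this needs a change in distribution shape and is not the expected case.

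**A pilot.** Section 11 says the study is not fully powered for all analyses. This limits the consequence but does not excuse an unexplained change of a primary outcome.

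**Conclusion.** The concern holds, and it should be fixed. The SAP's primary hypoglycemia outcome differs from the protocol's measure, no reason is given that could explain it, and reading 60 as 70 closes only part of the gap. This conclusion needs no model.

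The size does need one. Under the assumed distributions the printed band leaves uncounted 79-85% of time below 70 (log-normal) or 80-82% (gamma). A 54-70 band would leave out 8-30% or 23-46%. These are illustrations, and the trial's own CGM data would replace them. The section 11 detectable difference cannot be quoted for either band. No claim is made that diet comparisons would reverse.

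**What to change.** Amend the SAP, with a date and a reason, so that the primary outcome is percent of CGM time below 70 mg/dL over the 14-day wear, as in section 11. State whether the 10-minute condition in section 8a applies to percent time or only to counting episodes. If another range is intended, state it and justify the departure from sections 8a and 11.

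Two optional additions would help: reporting time below 54 and time at 54-69 as components, and keeping 54-60, if at all, only as a labelled exploratory item.

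The cost is a short SAP amendment and a calculation (or a re-run, if the analysis has been done) on CGM data the trial already collects. No new data are needed.
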